15 STATISTICAL ANALYSIS & DATA MANAGEMENT

Data on the clinical and non-clinical risk factors will be summarized using means, standard deviations (SDs) and percentages. Successful left atrial appendage closure will be reported as a percentage

Table 1. Patient screening tool

1. Atrial fibrillation or atrial flutter documented? Yes No
 Paroxysmal Short-lasting persistent Longstanding persistent

2. EP consultation to exclude candidacy for ablation? Yes No
 catheter or surgical

3. CTA obtained to assess LAA anatomy? Yes No
 If yes, was anatomy favorable for this procedure? Yes No
 If no, justification for procedure:

If no, was second opinion obtained? Yes No
 Physician rendering second opinion: _____

4. CHADS₂-VASC score _____ of 9
 a. CHF _____ of 1
 b. Hypertension _____ of 1
 c. Age >65 yrs _____ of 1
 d. Diabetes Mellitus _____ of 1
 e. Stroke or TIA _____ of 2
 f. Vascular Disease _____ of 1
 g. Age >75 _____ of 1 (in addition to age>65)
 h. Sex Category _____ of 1 (Male=0; Female =1)

5. CHADS₂ score: _____ of 6
 a. CHF _____ of 1
 b. Hypertension _____ of 1
 c. Age >75 yrs _____ of 1
 d. Diabetes Mellitus _____ of 1
 e. Stroke or TIA _____ of 2

6. HAS-BLED SCORE _____ of 9
 a. Hypertension _____ 1
 b. Abnormal renal and hepatic function ² _____ 1-2
 c. Stroke _____ 1
 d. Bleeding tendency/predisposition³ _____ 1
 e. Labile INRs on warfarin⁴ _____ 1

¹Systolic BP >160 mmHg

²Renal: serum creatinine >2.25 mg/dl
 Hepatic: Bili 2-3x normal and
 AST/ALT/ALK-P >3x normal or chronic
 disease (cirrhosis)

³History of bleeding or anemia

⁴Time in therapeutic range <60%

⁵Concomitant antiplatelet or NSAID use or
 excess alcohol

f. Elderly (>65 yr) 1
g. Drugs or alcohol (1 point each)⁵ 1-2

6. If CHADS₂-VASC score<3, or if HAS-BLED score is <3, list justification for procedure:

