5.2 Left Atrial Appendage Closure Procedure

The following information will be collected at the time of Procedure

1. TEE evidence of LAA closure
2. Angiographic confirmation of LAA closure
3. Presence/absence of pericardial effusion
4. Amount (# ml) of pericardial drainage
5. X-ray exposure
6. Total amount of contrast used
7. Adverse Events Assessment
8. Assessment

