5.3 Follow-up Visits

5.3.1 7 days Post Procedure(-3/+10)

1. Interim history and physical examination
2. Cardiac Medications
3. Chest X-Ray

5.3.2 90 days post procedure (-15/+15)

1. Interim history and physical examination
2. Cardiac Medications
3. Chest X-Ray

5.3.3 180 days Post Procedure (-30/+30)

1. Interim history and physical examination
2. Cardiac Medications
3. Chest X-Ray

4. Either Cardiac computed tomography angiography (CCTA) or Transesophageal Echocardiogram (TEE) to be completed to confirm LAA closure

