9. ENROLLMENT

Subjects consented will be tracked by the study team and will be considered enrolled in this study at the time of the start of their left atrial appendage closure procedure. All subjects that are consented who do not undergo left atrial appendage closure with SentreHeart Lariat® will be considered screen failures. Any patients that have a failed attempt at left atrial appendage closure with SentreHeart Lariat® will be tracked through their index hospitalization for safety; their study follow up will be complete at the time of discharge.

Subjects that are approached will be given ample time to assure that this population has the opportunity to carefully read the consent, share the information with family members, and discuss the objective of the study along with any risks/benefits that may be expected. Subjects will have all of their questions answered before signing the consent and taking part in the study. Additionally, information on how to contact the study doctor will be provided in the consent form.

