9.3 Screening/Enrollment Log

A log will be maintained that documents subjects screened and those enrolled.

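### Section 15 gives the closure percentage no denominator, time point or success criterion, so a rate omitting failed attempts is permitted; Section 11 also ends participation before the 180-day closure image

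*Combined protocol and SAP*

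**What the plan says.** Section 2 lists successful closure as a secondary aim. The only analysis rule for it is in Section 15: "Successful left atrial appendage closure will be reported as a percentage".

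Closure is assessed at two times. At the procedure, Section 5.2 collects both "TEE evidence of LAA closure" and "Angiographic confirmation of LAA closure". At 180 days, Section 5.3.3 asks for one of two modalities: "Either Cardiac computed tomography angiography (CCTA) or Transesophageal Echocardiogram (TEE) to be completed to confirm LAA closure". The Section 6 matrix agrees.

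On who is counted, Sections 5 and 9 say that a consented subject "will be considered enrolled in this study at the time of the start of their left atrial appendage closure procedure". They continue: "All subjects that are consented who do not undergo left atrial appendage closure with SentreHeart Lariat® will be considered screen failures". The next sentence gives failed attempts their own rule. They are followed for safety during the index hospital stay, and "their study follow up will be complete at the time of discharge". Section 11 repeats this. Section 3 describes the cohort as the consecutive patients who undergo lone closure with the device. Section 9.3 adds: "A log will be maintained that documents subjects screened and those enrolled".

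On duration, Sections 3, 5.3.3, 6 and 7 run to 180 days (-30/+30). Section 11 ends a subject's participation once the 90-day assessments are done, or when the 90-day window closes, unless an out-of-window visit has been booked.

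**The concern.** A percentage cannot be interpreted without its denominator. Closure among subjects with a late image is a different quantity from closure among all patients taken to the procedure. The first is conditional on the procedure having worked, because the plan asks for no 180-day image after a failed attempt. If it were reported simply as the closure rate, a reader could not tell which quantity it was, and the plan does not require a label that would say so.

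Two features go beyond missing detail. First, the enrolment rule counts a failed attempt as an enrolled subject, whereas the screen-failure sentence and the cohort wording in Section 3 can be read to leave it out. The documents can therefore support two denominators even for the acute rate. Second, if Section 11 is followed as written, the only late closure image falls outside participation for subjects whose procedure succeeded as well. Closure is the only effectiveness result that Section 15 names, so both features bear on the registry's main descriptive figure for the device.

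**Working it through.** The plan states no expected closure rate, failure rate or sample-size derivation, so there is no figure of its own to reproduce. The cap of 50 subjects (Sections 3, 4 and 7) is the only count available.

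**Step 1: who has a 180-day image.** A started procedure ends either closed or as a failed attempt. Failed attempts leave at discharge, so they have no planned 180-day image. They are nevertheless known to the study: the procedure-day TEE and angiography results are collected, and the patients are tracked to discharge. A rate over all started procedures can therefore be computed from data already planned.

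**Step 2: effect of leaving failures out.** Let N be started procedures, f failed attempts, m subjects closed acutely but without a 180-day image, and k later leaks seen on the image. Only the cap N = 50 comes from the documents; f, m and k are assumptions.

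- Imaged only: (N − f − m − k)/(N − f − m)
- All started, missing counted as not closed: (N − f − m − k)/N
- All started, missing counted as closed: (N − f − k)/N

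With m = k = 0, the imaged-only rate is always 100% and the all-started rate is (N − f)/N. The difference is f/N, or 2 points per failure at N = 50.

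| f (assumed) | Imaged only | All started (exact 95% CI) | Difference |
|---|---|---|---|
| 0 | 50/50 = 100% | 50/50 = 100% | 0 points |
| 1 | 49/49 = 100% | 49/50 = 98.0% (89.4 to 99.9) | 2 points |
| 3 | 47/47 = 100% | 47/50 = 94.0% (83.5 to 98.7) | 6 points |
| 5 | 45/45 = 100% | 45/50 = 90.0% (78.2 to 96.7) | 10 points |
| 8 | 42/42 = 100% | 42/50 = 84.0% (70.9 to 92.8) | 16 points |

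**Step 3: effect of missing images.** The two all-started rates differ by m/N. With f = 5, m = 5 and k = 0 they are 40/50 = 80.0% (66.3 to 90.0) and 45/50 = 90.0% (78.2 to 96.7), while the imaged-only rate is 40/40 = 100%. The plan does not say which of the three would be reported.

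**Step 4: the two end dates.** The 90-day window closes at 90 + 15 = day 105. The 180-day window opens at 180 − 30 = day 150. Under Section 11, and apart from its out-of-window exception, a subject has left at least 150 − 105 = 45 days before the late image could fall in its window.

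**The case against.** The strongest reply is that no section plans a 180-day rate among imaged subjects, so the harm is conditional on a choice that nobody has announced. That stands. A reader might infer that the registry will drop its failures, and the documents do not support that. Enrolment at the start of the procedure, the use of the term failed attempt, and the procedure-day imaging all point towards a rate over every started procedure.

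A reader might also infer that failed attempts are formally screen failures. Read in sequence, Sections 5 and 9 do not say so. The sentence after the screen-failure rule treats failed attempts as a separate group with follow-up to discharge, and the more natural reading is that screen failures are subjects whose procedure never began. What remains is wording that can be read literally the other way. The log needs no category for failed attempts, because a log of enrolled subjects already covers them.

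The magnitudes are assumed, and with no failures and no missing images the denominator makes no difference. The Section 11 conflict affects all late follow-up, not only closure, so it does not make the denominator gap itself more serious. Finally, counting every absent image as not closed would merge deaths before 180 days with missed visits; the fix has to keep them apart.

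**Conclusion.** The point holds as an omission together with two inconsistencies. Section 15 leaves the denominator, time point and success criterion of its closure percentage unstated, and no other section supplies them. The plan permits a rate without the known failures but does not prescribe one. Section 11 contradicts Sections 3, 5.3.3, 6 and 7 on whether participation reaches the late image.

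The practical size is unknown. The figure of 2 points per omitted failure assumes 50 started procedures, complete imaging of the closed subjects and no later leaks; the number of failures is not given anywhere. Confidence is high that the gap exists, but not that it would be large. It is worth correcting, at the low end of severity, because closure is a secondary aim reported descriptively with no hypothesis test.

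**What to change.** 1. Reconcile Section 11 with the 180-day visit and image in Sections 3, 5.3.3, 6 and 7.
2. In Section 15, state the criterion for successful closure, including which procedure-time result is used if TEE and angiography disagree. Report acute and 180-day closure separately, each over all started procedures, with failed attempts counted as not closed and exact 95% confidence intervals.
3. For subjects closed acutely but without a 180-day image, report the number, with deaths separate from missed images. Show the 180-day rate with these subjects counted as not closed and again as closed, and label any imaged-only rate as such.
4. In Sections 5 and 9, limit screen failure to consented subjects whose procedure never started.

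The cost is wording in Sections 5, 9, 11 and 15. No new test is needed if the 180-day image stays in the plan, since the procedure-day results are already collected. If the sponsor instead settles on the 90-day end, there is no late image to report and Section 15 should give the acute rate only. The downside is that the closure rate may look less favourable, and counting missing images as not closed may understate true closure; showing both bounds makes that visible.
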